5.9 Duration of Follow Up

Patients will be followed until death and the follow-up information for trial reporting will be obtained either from the patient's medical records or through direct contact with the patient (i.e. clinic visit or phone call). The timing of these will be based on scheduling of clinical care for the treatment of the patient's cancer (i.e. clinic visits every 3 months, 6 months, yearly). Patients will be followed specifically for evidence of progression/recurrence based on imaging and survival.

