5.8 Off Study Treatment Visit

Within 1-2 weeks after the last day of study treatment, patients will have their last study specific clinical visit. At the discretion of the treating physician, the tests/procedures due to be performed at the Off Study Treatment visit may be performed on the last day of the CKM treatment for scheduling purposes.

AEs and conmeds will be collected for up to 5 days post last dose of treatment. Any patient experiencing study related SAE will be followed until resolution to Grade 1 or baseline.

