7. ADVERSE EVENTS: LIST AND REPORTING REQUIREMENTS

Adverse event (AE) monitoring and reporting is a routine part of every clinical trial. The following list of AEs (Section 7.1) and the characteristics of an observed AE (Section 7.2) will determine whether the event requires expedited reporting **in addition** to routine reporting.

Note that Phase 2 of this study will include two periods of immunotherapy, administered before and after adjuvant chemotherapy (minimum 5 day wash-out periods), in order to separate potential toxicities of the chemokine modulatory regimen (all three factors are short-acting), from the anticipated toxicities of adjuvant chemotherapy. For this reason, we will only collect the toxicity data from the periods of immunotherapy. All toxicities related to the vaccine or CKM must be followed until resolution to grade 1 or baseline.

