7.1 Adverse Events and Risks List(s)

7.1.1 DC Vaccine

Dendritic cell vaccines have been investigated extensively in a number of centers and to date, have not been reported to be associated with limiting toxicities or adverse side effects. DC vaccines carry a potential risk of development of autoimmune disease (such as lupus, or vitiligo). Whereas development of vitiligo has been reported with similar vaccines administered to melanoma patients (and correlated with positive response to vaccination), other side effects have not been reported. Although, based on previous trials with DC-based vaccines, the possibility of developing an allergic reaction to DC-based vaccines is rare there is a chance that patients could have an allergic reaction to the vaccine.

While other classes of immunotherapeutic drugs, particularly the currently approved immune checkpoint blocker, Yervoy [Ipilimumab] can produce significant toxicity, such as enterocolitis, hepatitis, dermatitis (including toxic epidermal necrolysis), neuropathy, and endocrinopathy, due to its ability to promote polyclonal T-cell activation and proliferation, such effects have not been described following application of DC cancer vaccines, including previously-administered alpha-DC1-based vaccines, their combinations with a long acting TLR3 ligand poly-ICLC (Okada,

Kalinski, Bartlett, J. Clin. Onc. 29 (3):330-336, 2011) or their combinations with the proposed CKM regimen in our patients treated on compassionate-use protocols.

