7.3 Recording/Reporting requirements

7.3.1 Eliciting AE Information

Research subjects will be routinely questioned about AEs at study visits.

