6. Peripheral blood for potential correlative studies will be collected at the following time points: once during the pre-screening, within 60 minutes before the vaccinations of the priming cycle, and booster cycles 1 and 2; and within 60 minutes after completing booster cycle 2 on Friday. Peripheral blood for potential correlative studies may additionally be drawn within 60 minutes before the vaccination of booster cycle 3 on Monday and within 60 minutes after completing booster cycles 1 and 3 on Friday.
7. Performed within 2 weeks prior to the priming dose of vaccine and 5 business days prior to cycles 1, 2 and 3 vaccines.
8. CT or MRI imaging should be performed prior to cycle 1 if the recovery period from surgery is greater than 6 weeks.
9. At the discretion of the treating physician, the tests/procedures due to be performed at the Off Study Treatment visit may be performed on the last day of the CKM treatment for scheduling purposes.
10. Performed as routine pre-operative evaluation.
11. AEs /conmeds should be collected up to 5 days after treatment, unless considered clinically significant or serious in nature in which case they will be followed until resolution or Grade 1.

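### No enquiry about new autoimmune disease is scheduled after the off-treatment visit, so the descriptive adverse event summary may undercount later onset (cheap improvement, low-to-modest severity)

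*Combined protocol and SAP*

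**What the plan says.** **The risk.** Section 7.1.1 states: "DC vaccines carry a potential risk of development of autoimmune disease (such as lupus, or vitiligo"). It gives no time to onset. It adds that vitiligo has been seen with similar vaccines "administered to melanoma patients (and correlated with positive response to vaccination), other side effects have not been reported".

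**Collection during treatment.** Section 5.8: "AEs and conmeds will be collected for up to 5 days post last dose of treatment". Section 10, footnote 11: "AEs /conmeds should be collected up to 5 days after treatment, unless considered clinically significant or serious in nature"; events of that kind are followed until they resolve or reach Grade 1. Section 7.3.1: "Research subjects will be routinely questioned about AEs at study visits". The introduction to Section 7: "we will only collect the toxicity data from the periods of immunotherapy". The reason it gives is to keep the toxicity of the short-acting CKM agents apart from that of chemotherapy. Its final sentence requires every toxicity related to the vaccine or CKM to be followed to grade 1 or baseline.

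**After treatment.** Section 5.8: "Within 1-2 weeks after the last day of study treatment, patients will have their last study specific clinical visit". From then until death, follow-up comes from medical records, clinic visits or phone calls. Section 5.9 gives its content: "Patients will be followed specifically for evidence of progression/recurrence based on imaging and survival".

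**Reporting.** Section 13.3 plans a descriptive summary of all adverse events by grade, frequency and attribution.

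**The concern.** The protocol names one harm, autoimmune disease, that need not appear within days of a dose. Yet its scheduled questioning stops soon after the last dose. The reason given for limiting toxicity data concerns the CKM agents and does not discuss the vaccine. Section 3.2.2 also admits patients with indolent or chronic autoimmune disease not treated with steroids, so worsening of existing disease is possible as well as new disease.

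Safety is part of the primary objective (Section 1.1). For autoimmune disease, the Section 13.3 summary would combine active questioning during treatment with whatever happens to be reported afterwards. A low or zero count could not be read as a rate over the whole of follow-up.

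**Working it through.** The plan gives no figure to reproduce. The check is a reading of every place where an autoimmune event could be captured, then date arithmetic for the length of routine collection.

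**1. Routes into the record**

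| Onset | Route | Scheduled question? |
|---|---|---|
| During a cycle, or between cycles | Questioning at the study visit or next booster (7.3.1, Section 10) | Yes |
| Within the window, vaccine-related, still present | Followed to grade 1 or baseline (Section 7 introduction) | Follow-up required |
| After the window, patient given extra vaccine | Adverse event check on vaccination days (5.5) | Yes, on those days |
| After the window, any seriousness | Recorded if observed or volunteered (7.3.2) | No |
| After the window, thought reasonably or probably due to the drug | Investigator report to the sponsor, not limited to serious events (7.6) | No |
| After the window, serious and unexpected | FDA and IRB reporting (7.7, 7.8) | No |

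Footnote 11 lets clinically significant or serious events run past 5 days, but it does not create an enquiry about new ones. The gap is therefore confined to new onset after the off-treatment visit in patients not receiving extra vaccine.

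**2. When routine collection ends, in days after priming**

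Formula: (Monday of last booster − priming day) + 4 days to the Friday of CKM + 5 days. Inputs are Sections 5.1, 5.2, 5.8 and 10.

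- Calendar weeks 1, 4, 8, 12: 77 + 4 + 5 = 86
- Section 5.2 target, three gaps of 4 weeks: 84 + 4 + 5 = 93
- Longest permitted gaps, three of 12 weeks: 252 + 4 + 5 = 261
- If events are also taken at an off-treatment visit 14 days after treatment: 77 + 4 + 14 = 95; 84 + 4 + 14 = 102; 252 + 4 + 14 = 270
- Phase 1, one booster: 21 + 4 + 5 = 30, or 21 + 4 + 7 = 32 by the Section 5.1 observation period

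These are typical spans, not upper limits. Cycles given outside the windows (5.2) and extra vaccine (5.5) lengthen them.

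**3. Set against planned follow-up (Phase 2)**

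Section 13.2 plans 1.5 years after accrual closes, taken as 548 days. Where that clock starts for the last patient is an assumption, so both choices are shown for a patient who stays under follow-up.

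- Clock at priming: 86/548 = 15.7% to 270/548 = 49.3%. Uncovered: 548 − 270 = 278 to 548 − 86 = 462 days.
- Clock at surgery, priming 6 to 16 weeks (42 to 112 days) later: 548 − 112 = 436 to 548 − 42 = 506 days remain. 86/506 = 17.0% to 270/436 = 61.9%. Uncovered: 436 − 270 = 166 to 506 − 86 = 420 days.

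These are shares of calendar time. Turning them into shares of events needs a latency distribution, and the documents give none.

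**The case against.** The case for leaving the plan alone has substance.

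- **The risk is described as little observed.** Section 7.1.1 calls it potential and reports only vitiligo, in melanoma patients given similar vaccines. That autoimmune disease would appear late is not stated anywhere. This stands, and it limits the claim to a possible undercount.
- **Capture does not stop at day 5.** A reader might infer that autoimmune disease arising after the window is excluded from the record, or that only serious disease would be picked up. The documents support neither. Section 7.3.2 covers observed or volunteered events of any seriousness and sets no time limit. Section 7.6 covers any adverse effect reasonably or probably due to the drug. Slowly evolving vaccine-related disease that starts within the window must be followed. What remains is that these routes depend on someone noticing and reporting; none is a scheduled question about new onset.
- **The window is already stated.** Sections 5.8 and 10 define it for the trial, so repeating it in Section 13.3 would be editorial. This stands.
- **No decision turns on it.** Late events in a single-arm trial with intercurrent chemotherapy can be described but not compared. This also stands, and it keeps the severity low to modest. It does not remove the case for a nearly free improvement to a safety objective.

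**Conclusion.** The point holds in a limited form. After the off-treatment visit no enquiry about new autoimmune onset is scheduled, except on days of extra vaccination, although the protocol names that risk. The descriptive summary in Section 13.3 may therefore undercount autoimmune disease that begins after the window.

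The size of any undercount cannot be given. A reader might take the 16% to 62% of calendar time covered as the share of events captured. That would be wrong without incidence and latency, and the percentages also depend on the assumed start of the 548-day clock and on patients completing three boosters within the permitted gaps.

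The TTP test, the RP2D and the RLT boundary are unaffected. Severity is low to modest; the reason to act is that the remedy is cheap.

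**What to change.** - In Section 5.9, add new or worsening autoimmune disease to the items taken at each existing record review or contact. Record onset date, grade, attribution and any intercurrent chemotherapy.
- In Section 13.3, report these events separately and descriptively, counted from first vaccine, with follow-up time shown.
- Leave the 5-day window for all other adverse events as it is.

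The cost is modest data entry, a possibly less favourable harm count, and uncertain attribution for late events. No new visit, test or patient is needed, and sample size, power and alpha do not change.

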5.10 Duration of Study

Patients will be removed from study if any of the criteria below applies.

- Patient decides to withdraw from the study.
- Patient removed due to non-compliance.
- The investigator decides to prematurely close the trial.

The reason for study removal and the date the patient was removed must be documented.

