5.7 Duration of Study Treatment

In the absence of treatment delays due to adverse event(s), treatment may continue until one of the following criteria applies:

- Disease progression (excluding disease progression during the time between surgery and the CKM regimen, these patients will be allow to continue with study treatment). See also Section 5.5.
- Patient withdraws consent but allows continued follow-up for survival
- Patient non-compliance
- Unacceptable agent specific adverse event(s).
- General or specific changes in the patient's condition render the patient unacceptable for further treatment in the judgment of the investigator/sub-investigator.
- Pregnancy in patient

The reason and date a patient was removed from study treatment must be documented.

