13.2 Power and Sample Size for the Study of Efficacy

Based on information from our prospective database at the University of Pittsburgh over the last 10 years, we expect to treat ~ 115 patients per year (malignant peritoneal mesothelioma ~ 15 cases/year; appendiceal peritoneal carcinomatosis ~ 40 cases/year; colorectal carcinomatosis ~ 60 cases/year). We anticipate approximately 50% of treatment patients will participate in the clinical trial. A review of the literature demonstrates median time-to-progression of 20 months, 20 months and 12 months for malignant peritoneal mesothelioma, appendiceal peritoneal carcinomatosis, and colorectal carcinomatosis, respectively. We aim to demonstrate a 25% improvement in time-to-progression (malignant peritoneal mesothelioma 25 months; appendiceal peritoneal carcinomatosis 25 months; and colorectal carcinomatosis 15 months). We will need 168 patients over 3 years of accrual with an additional 1.5 years of follow-up after accrual ceases. This will provide 90% power to detect an overall improvement of 25% for an exponential test at alpha = 0.10.

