13.3 Data Analysis

At the completion of follow-up in evaluable patients, we will estimate progression-free survival by the Kaplan-Meier method with Greenwood 90% confidence intervals. We will conduct a formal test of the hypothesis that progression-free survival is improved with the experimental therapy. This test will be a one sided exponential test at $\alpha = .10$ that the median progression-free survival is better than 25% compared to historical controls. If this test is significant we will conclude that the progression-free survival is improved compared to the historical control. Descriptive summaries will be prepared of all adverse events by grade, frequency and attribution. An assessment of the association between immune parameters and survival will be conducted. The panel of immune parameters will be tested for association with progression-free and overall survival with Cox proportional hazards regression.

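### Non-compliance ends treatment only in 5.7 but study participation in 5.10, so the progression and survival follow-up promised in 5.9 is not secured for these patients

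*Combined protocol and SAP*

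**What the plan says.** Section 5.7, on the duration of treatment, lists "Patient non-compliance" as a reason to stop study treatment. The same list has the item "Patient withdraws consent but allows continued follow-up for survival".

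Section 5.9 states no exception: "Patients will be followed until death". It also fixes the content: "Patients will be followed specifically for evidence of progression/recurrence based on imaging and survival". The information comes from medical records or direct contact, timed by routine care.

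Section 5.10 says that patients leave the study if any of its criteria applies. One is the patient's decision to withdraw; another is "Patient removed due to non-compliance".

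Section 3 replaces patients who are excluded or resign, and permits but does not require their continued follow-up.

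Time to progression is the primary efficacy endpoint (13.1.1) and overall survival is secondary (13.1.2). For the efficacy analysis, 13.3 says: "This test will be a one sided exponential test", against historical controls. It is done in 'evaluable' patients, a term that 13.3 does not define, and no censoring rule is given for patients who leave.

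**The concern.** One event has two consequences, and nothing tells site staff which applies. Non-compliance is not defined, so the choice between ending treatment and ending participation is a judgement made during an open, single-arm trial.

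If patients who stop complying have a worse prognosis than the rest, ending their follow-up removes progressions that would otherwise have been counted. No concurrent arm suffers the same loss, so any bias goes straight into the comparison with the historical value, in the favourable direction. Overall survival is exposed in the same way under 5.10. An analysis rule can be corrected later; a progression date that was never collected may not be recoverable.

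The withdrawal item in 5.7 adds a smaller gap: it names survival follow-up and is silent on progression, the primary endpoint.

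**Working it through.** **1. The sections side by side**

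| Section | What happens on non-compliance | Follow-up for progression and survival |
|---|---|---|
| 5.7 | Treatment stops | Not addressed for this item |
| 5.9 | No exception made | Required until death |
| 5.10 | Removed from the study | Not stated; removal conflicts with 5.9 |
| 3 | Not named (covers patients excluded or resigning) | Optional |

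**2. The plan's own sample size**

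Inputs from 13.2: "We will need 168 patients over 3 years of accrual with an additional 1.5 years of follow-up after accrual ceases", giving "90% power to detect an overall improvement of 25% for an exponential test at alpha = 0.10". Historical medians are 20, 20 and 12 months, and the expected case mix is 15 : 40 : 60. I assume that the enrolled mix equals this.

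- Events needed, one-sided: (1.2816 + 1.2816)² / (ln 1.25)² = 131.9.
- Event probability with uniform accrual A = 36 and further follow-up F = 18 months: 1 − [exp(−λF) − exp(−λ(A+F))] / (λA), with λ = ln 2 / median. This gives 0.694 for a median of 20 months and 0.851 for 12 months. Weighted: (55/115)(0.694) + (60/115)(0.851) = 0.776.
- N = 131.9 / 0.776 = 170, close to the stated 168. With 168 patients, 168 × 0.776 = 130 events are expected under the null, and power is 89.7%.

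This reproduces the plan with no allowance for dropout.

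**3. Upper bound on the bias**

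Suppose a fraction f of the events is lost and exposure is unchanged, meaning that each lost patient would have progressed just after removal. The estimated median is multiplied by 1/(1−f). The test statistic shifts by ln[1/(1−f)] × √[d(1−f)], with d = 130. The values of f are assumptions.

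| f | Median inflated by | Shift | Type I error (nominal 0.10) |
|---|---|---|---|
| 2% | 2% | 0.228 | 0.146 |
| 5% | 5% | 0.570 | 0.238 |
| 10% | 11% | 1.140 | 0.444 |

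**4. Milder mechanisms**

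Simulation under the null used 20,000 trials per setting. Progression follow-up of the removed patients stops at 4 months, and their hazard is a multiple of the others'. Hazards are scaled so that the average equals the historical rate.

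| Patients lost | Hazard multiple | Rejection rate, full follow-up | Rejection rate, with loss |
|---|---|---|---|
| 5% | 1.5 | 0.106 | 0.136 |
| 10% | 1.5 | 0.116 | 0.183 |
| 10% | 2 | 0.177 | 0.312 |
| 20% | 2 | 0.247 | 0.550 |
| 5% to 20% | 1 | 0.094 | 0.092 to 0.094 |

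Full follow-up exceeds 0.10 in the first four rows because mixed hazards break the exponential assumption. The effect of the loss is the gap between the last two columns. Here the loss is a fraction of patients, while f in step 3 is a fraction of events, so the two tables compare only approximately.

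**5. Loss of precision**

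If 5%, 10% or 20% of patients gave no progression data at all, power at 168 would fall from 89.7% to 88.5%, 87.2% or 84.1%. The cost in power is modest. The possible bias matters more.

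**The case against.** The strongest reply is that this is a wording inconsistency with no demonstrated consequence. Several parts of that reply stand.

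- A reader might infer that progression is certainly lost in these patients. The documents do not say so. Section 5.10 asks for the reason and date of removal and never says that record review stops. Section 3 permits continued follow-up of patients who are excluded or resign, and 5.9 draws on medical records. What can be said is that follow-up is not secured. Optional follow-up, decided case by case, can itself be selective.
- A reader might infer that the 5.7 withdrawal item discards progression data. It is a reason for stopping treatment, not a data rule, and is only silent on progression. Ending data collection after full withdrawal is not an error.
- Section 5.2 excludes from the primary efficacy analysis patients who miss a treatment window. Section 5.5 keeps removed subjects out of formal efficacy, although its paragraph concerns continued vaccine and its reach is arguable. After the off-treatment visit in 5.8 there are no study-specific visits, so non-compliance would arise mainly during treatment. Many such patients may already be outside the primary analysis, contributing neither events nor exposure. The formula in step 3 does not describe them.
- The figure of 44% is a ceiling. At the plan's historical medians an average-risk patient has a 10% to 16% chance of progressing in any 3 months (1 − 2^(−3/20) and 1 − 2^(−3/12)), far from the certainty that step 3 assumes. Nothing in the documents shows that non-compliant patients here have a worse prognosis.

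None of this removes the conflict between 5.10 and 5.9. The permissive sentence in Section 3 does not settle it either.

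**Conclusion.** The conflict is real and should be corrected. Section 5.10 removes non-compliant patients from a study in which 5.9 promises to follow everyone until death, and follow-up is at best optional for them.

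The size cannot be determined, because the documents state no loss rate. If the affected patients are kept in the primary analysis, type I errors of 15%, 24% and 44% (2%, 5% and 10% of about 130 events) are an upper bound. With 5% to 10% of patients lost at 4 months and a hazard 1.5 times that of the others, the rejection rate rises from 0.11–0.12 to 0.14–0.18. With removal unrelated to prognosis there is no inflation. Every loss fraction and hazard multiple here is an assumption.

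A reader might also infer that restoring follow-up would remove the bias from the primary test. It would not do so alone. Patients excluded under 5.2 or 5.5, or by the undefined 'evaluable' set in 13.3, would remain outside that test.

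**What to change.** - In 5.10, delete the non-compliance item. Patients who stop treatment for non-compliance then stay in 5.9 follow-up for progression and survival, through records and routine scans.
- In the 5.7 withdrawal item, write 'follow-up for progression and survival', so that the primary endpoint is covered when the patient permits it.
- Keep full withdrawal of consent to follow-up as the only patient-level reason to end data collection.

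The cost is two lines in an amendment, a check of the consent wording, and record review for the patients concerned. No new visits or scans are needed, because 5.9 already relies on records, telephone contact and routine care.

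The change secures overall survival and any analysis of time to progression that includes these patients. The exclusions in 5.2 and 5.5, the meaning of 'evaluable', and the missing censoring rule in 13.3 need their own correction.
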